## FLOW CHART

	Screening	Intervention
Period	(-t1)	(t1)
Enlistment		
informed consent	x	
inclusion/exclusion criteria	x	
Administration of the intervention		
biological sample collection *		x
phenotypic data collection **		x

(\*) the biological sample has already been previously collected in the context of the SERENA, REASON or LIVER-BIBLE studies

(\*\*) These are data previously collected in the context of the SERENA, REASON or LIVER-BIBLE studies

## LIST OF ABBREVIATIONS

**THERE IS:**Ethics Committee

**THERE:**Informed Consent

**CRF:**Case Report Form, data collection form

**GCP:**Good Clinical Practice, good clinical practice

**WGS:** Whole Genome Sequencing

**MASLD:** Metabolic dysfunction-associated steatotic liver disease

**HCC**Hepatocellular Carcinoma

**LoF**Loss of function

**CHIP:** Clonal hematopoiesis of indeterminate potential

**PRSP**Polygenic risk score

**AST:** Aspartate aminotransferase

**ALT:** Alanine aminotransferase

**GGT**Gamma-glutamyl transferase

9.8.2 Publications and Intellectual Property Rights on the Results of the Study

**10. Indemnity and compensation in case of damages**

**11. Financial agreements**

**12. Disclosure on conflicts of interest**

**13. References**

## 1. INTRODUCTION

### 1.1 Background and rationale

Metabolic Dysfunction-Associated Steatotic Liver Disease (MASLD) is a leading cause of chronic liver disease globally, with a prevalence exceeding 30% in the population. MASLD is closely associated with insulin resistance and cardiometabolic conditions and, in 20-30% of cases, can progress to steatohepatitis (MASH), which is characterized by progressive liver damage and inflammation [1]. In patients at highest risk, the disease can lead to the onset of advanced fibrosis, cirrhosis and hepatocellular carcinoma (HCC). One of the main problems in the clinical management of MASLD is the absence of specific risk biomarkers and the lack of effective treatments, especially for patients with advanced stage disease [2]. MASLD has a large and well-documented genetic component, with studies identifying several common variants associated with this pathology, such as those in the PNPLA3, TM6SF2 and MBOAT7 genes [3]. However, these variants identified so far explain only a small part of the heritability of MASLD, also suggesting the contribution of rare loss-of-function (LoF) variants [4-5]. Furthermore, scientific evidence indicates that the accumulation of somatic variants, both in hepatocytes and myeloid cells, could also play a key role in the progression of MASLD [6]. In particular, clonal hematopoiesis of indeterminate potential (CHIP), which is a condition characterized by the presence of hematopoietic clones with somatic mutations often associated with leukemia and cardiovascular diseases [7], could favor the onset of hepatocellular carcinoma [8]. However, the evidence available to date is still limited and requires further investigation and studies on larger cohorts.

The study in question therefore aims to further investigate this aspect by analyzing the genetic profile using a Whole-Genome Sequencing (WGS) approach; peripheral blood DNA samples from patients with advanced MASLD and peripheral blood DNA samples from controls presenting various associated metabolic risk factors will be sequenced.

Additionally, 80 liver tissue samples from patients with advanced MASLD will be sequenced to identify specific somatic mutations. Expected outcomes of this study include the identification of novel genetic variants associated with MASLD progression, improved risk stratification through the development of polygenic risk scores, and the identification of potential therapeutic targets. This

study represents a fundamental step in understanding the biology of MASLD and could have important clinical implications for disease management.

## **2. OBJECTIVE/S/HYPOTHESIS OF THE EXPERIMENTATION**

A careful review of the scientific literature shows that MASLD has a strong genetic component, but the evidence available to date only partially explains the predisposition to the advanced form of the disease. Furthermore, it is known that somatic variants, particularly clonal hematopoiesis of indeterminate potential (CHIP), may contribute to the progression of MASLD to cirrhosis and hepatocellular carcinoma (HCC).

### 2.1 Primary objective

The primary objective of this study is to identify genetic variants (germline and/or somatic) associated with the risk of developing advanced MASLD (fibrosis  $\geq 2$  and/or hepatocellular carcinoma) in the Italian population.

### 2.2 Secondary objectives

The secondary objectives of this study are:

- To characterize the contribution of somatic variants (in hepatocytes and hematopoietic cells) that are involved in the progression of advanced MASLD;
- Evaluate and develop polygenic risk scores (PRS) for risk stratification and identification of specific subphenotypes;
- To study the associations between genetic variants and metabolic phenotypes related to MASLD;
- Identify relevant therapeutic targets for the development of precision medicine strategies in advanced MASLD.

## **3. STUDY DESIGN**

### 3.1 Study design

The proposed study is a single-center, national, non-pharmacological interventional study with genetic analysis and is non-profit.

The total number of samples for which Whole Genome Sequencing (WGS) is planned is 2880, distributed as follows:

- 800 peripheral DNA samples from patients with advanced MASLD attending the Fondazione IRCCS Ca' Granda Ospedale Maggiore Policlinico and collected as part of the SERENA study (study promoted by the Fondazione IRCCS Ca' Granda Ospedale Maggiore Policlinico, approved by the CE Milano Area2 on 07.26.2017);
- 2000 peripheral DNA samples from controls presenting metabolic risk factors collected as part of the Liver-BIBLE study (a study promoted by the Fondazione IRCCS Ca' Granda Ospedale Maggiore Policlinico, approved by the CE Milano Area2 on 01.07.2020);
- 80 pathological liver tissue samples isolated from patients with advanced MASLD in the context of the REASON clinical study (study promoted by the Fondazione IRCCS Ca' Granda Ospedale Maggiore Policlinico, approved by the CE Milano Area2 on 07.07.2021);

### 3.2 Inclusion criteria

Specific inclusion criteria for patients with advanced MASLD:

- Patients with advanced MASLD defined as liver fibrosis  $\geq 2$  and/or development of HCC;
- patients enrolled in the SERENA study and where applicable also in the REASON study;
- Liver biopsy for suspected non-alcoholic steatohepatitis (NASH) at the time of diagnosis;
- Cholecstectomies
- age [40-70 years]
- patients who have signed the informed consent

Specific inclusion criteria for control group:

Blood donors from the LIVER-BIBLE study aged between 40 and 70 years in the presence of overweight or obesity (Body mass index-BMI $>25\text{Kg/m}^2$ ) and at least two of the following risk factors:

- impaired fasting blood glucose or diabetes mellitus (blood glucose  $\geq 100 \text{ mg/dl}$ )

- dyslipidemia (triglycerides $\geq$ 150mg/dl, HDL $<$ 45/55 in M/F)
- arterial hypertension

### 3.3 Exclusion criteria

Specific exclusion criteria for patients with advanced MASLD:

- Positivity for chronic viral hepatitis (HCV-RNA and/or HBsAg);
- Positivity for other liver diseases such as autoimmune and viral hepatitis (hepatitis B and C), hereditary hemochromatosis, alpha-1-antitrypsin deficiency, Wilson's disease.

Specific exclusion criteria for the control group:

Subjects suffering from chronic degenerative diseases will be excluded, with the exception of well-controlled hypertension and type 2 diabetes mellitus not requiring pharmacological therapy (as is already common practice for eligibility to donate blood) and donors aged  $>$  65 and  $<$  40.

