### **4.2 Sample and data collection**

Our research is based on two fundamental pillars, represented by rigorously selected study cohorts.

The SERENA project involves 800 patients with advanced MASLD, whose peripheral blood DNA will be sequenced (WGS, 20x coverage). To further deepen our understanding of disease progression, a subset of 35 of these patients will undergo even more detailed analysis: we will sequence at 50x 80 pathological liver tissue samples from the REASON study, including samples with advanced fibrosis and, where present, hepatocellular carcinoma (HCC).

On the control side, the Liver-BIBLE Milano project offers us a valuable cohort of 2,000 individuals matched by sex and metabolic risk factors. These participants are selected from blood donors aged 40 to 70 years who meet at least two criteria for metabolic syndrome. Their phenotypic characterization is extremely thorough, ranging from anthropometric assessment to metabolic and inflammatory profiles, from noninvasive liver injury diagnostics to OMICs analysis. This integrated approach, combining genetic and clinical data from well-defined cohorts, will allow us to conduct robust comparisons between cases and controls, significantly advancing our understanding of advanced MASLD.

Specifically, biological samples will be collected as follows:

- Peripheral Blood: Peripheral blood DNA samples will be collected from all 800 MASLD patients and all 2000 metabolic controls.
- Pathological Liver Tissue: A total of 80 pathological liver tissue samples will be collected from a subset of 35 patients with advanced MASLD. These samples will be derived from the REASON study and will include tissue with advanced fibrosis (n=30) and, when present, hepatocellular carcinoma (HCC) samples (n=12).

Clinical and phenotypic data associated with the biological samples collected:

- For Patients with Advanced MASLD, aimed at understanding the progression of the disease, its complications and related factors:

- Detailed Clinical Phenotype: Includes a detailed medical history focused on the history of MASLD, including diagnosis, progression, presence and severity of specific symptoms, history of pharmacological or surgical treatments, and relevant comorbidities, particularly metabolic and cardiovascular ones.

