- Biomarkers of Liver Injury and Function: Liver enzymes such as alanine aminotransferase (ALT), aspartate aminotransferase (AST), gamma-glutamyl transpeptidase (GGT), and alkaline phosphatase (ALP) levels, indicators of hepatocellular injury or cholestasis.
- Liver synthetic function: Bilirubin, albumin, prothrombin time/INR, which reflect the liver's synthetic capacity.
- Non-invasive biomarkers of liver damage: data from tools such as Fibroscan or predictive score calculations (e.g., FIB-4, NAFLD Fibrosis Score) to assess the presence and degree of steatosis, steatohepatitis (NASH), fibrosis, and cirrhosis.
- Metabolic Risk Factors: such as data on glucose, lipids (total cholesterol, HDL, LDL, triglycerides), insulin, HbA1c and indices of insulin resistance (e.g. HOMA-IR), which are essential for outlining the metabolic profile underlying MASLD.
- Inflammatory Biomarkers: Such as C-reactive protein (CRP) and ferritin, useful for assessing systemic and/or hepatic inflammatory status.
- Hepatocellular Carcinoma (HCC) Data: For patients who have developed HCC, specific information on diagnosis, staging, oncological treatments and follow-up is collected, essential for studying clonal evolution.

- For Metabolic Controls, aimed at providing an extremely in-depth baseline characterization of their general health and metabolic risk profile, in the absence of advanced MASLD, to serve as a robust comparison:
  - Detailed Anthropometric Assessment: Height, weight, waist circumference, BMI, for a precise quantification of adiposity.
  - Detailed Medical History: Lifestyle, eating habits (diet), complete medical history, with particular attention to the presence of metabolic risk factors (hyperglycemia, hypertension, dyslipidemia, increased adiposity) which are inclusion criteria.

- Complete Blood Count: Evaluation of the cellular components of the blood.
- Coagulation Parameters: Includes factors such as FVIII, VWF, protein C (PC) and D-dimer.
- Standard Clinical Biochemistry: Includes assessments of general liver and renal function, as well as inflammatory biomarkers.
- Complete Metabolic Profiles: Glucose, lipids (total cholesterol, HDL, LDL, triglycerides), insulin and HbA1c, to quantify metabolic risk factors.
- Liver Biomarkers: Although not targeted to progression of advanced MASLD, baseline biomarkers of liver function are included to ensure the absence of significant non-MASLD liver disease.

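### Chronic disease is screened out of the donor controls but not out of the cases, so any case-donor comparison of clonal haematopoiesis (CHIP) is biased towards a positive association

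*Protocol*

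**What the plan says.** **Who the controls are.** Protocol section 3.2 takes them from a donor cohort: "Blood donors from the LIVER-BIBLE study aged between 40 and 70 years", with overweight or obesity and at least two metabolic risk factors. Section 3.3 then adds: "Subjects suffering from chronic degenerative diseases will be excluded, with the exception of well-controlled hypertension"; type 2 diabetes managed without drugs is the other exception. It ties this rule to ordinary eligibility to donate blood.

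**Who the cases are.** The case exclusions in section 3.3 are all hepatic: chronic viral hepatitis, autoimmune hepatitis, haemochromatosis, alpha-1-antitrypsin deficiency and Wilson's disease. No cardiovascular, haematological or general chronic disease excludes a case. Section 4.2 expects comorbidity in cases, since the data to be collected include "history of pharmacological or surgical treatments, and relevant comorbidities, particularly metabolic and cardiovascular ones". For patients with HCC, "specific information on diagnosis, staging, oncological treatments and follow-up is collected".

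**What CHIP is said to be linked to.** Section 1.1 describes CHIP as "hematopoietic clones with somatic mutations often associated with leukemia and cardiovascular diseases".

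**What will be compared.** The primary objective (section 2.1) covers germline and/or somatic variants and the risk of advanced MASLD. A secondary objective (section 2.2) is: "To characterize the contribution of somatic variants (in hepatocytes and hematopoietic cells) that are involved in the progression of advanced MASLD". The primary endpoint (section 5.1) is germline only. The somatic endpoint (section 5.2, item 1) names HCC as the outcome and states no comparison group.

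**The concern.** One group has been screened for diseases that the protocol's own rationale associates with CHIP, and the other has not. If people with those diseases carry CHIP more often, removing them from the controls alone lowers CHIP frequency there and leaves it untouched in the cases. An excess in cases then appears even when CHIP has nothing to do with the liver.

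Blood is the only tissue sequenced in both groups, because the 80 liver samples come from cases alone. CHIP is thus the only somatic measure on which cases and controls can be compared at all. An excess produced by eligibility could be reported as a contribution of CHIP to advanced MASLD.

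The selection is fixed by eligibility, so a later analysis plan cannot remove it simply by adding a cardiovascular covariate: controls with the disease are nearly absent by design, and the model would have little to adjust with.

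**Working it through.** **The plan's own figure.** There is none for CHIP: no prevalence, comorbidity rate, effect size or significance level. The power figures in section 6.1 concern germline variants and do not bear on this point.

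**Inputs from the protocol.** 800 cases and 2,000 controls (sections 3.1 and 6.1), a ratio of 2.5 controls per case.

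**Assumed inputs.**
- *b*, CHIP prevalence in people without cardiovascular disease: 5% or 10%.
- *s*, share of cases with cardiovascular disease: 10%, 20% or 40%. The share in controls is taken as zero.
- *R*, OR between CHIP and cardiovascular disease: 1.5 to 2.5, with 1.3 as a milder value.
- Two-sided significance level for CHIP: 0.05.
- No true link between CHIP and MASLD.

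**Formulas.**
- CHIP prevalence in cases with cardiovascular disease: p1 = R·b / (1 − b + R·b)
- CHIP prevalence in all cases: pc = (1 − s)·b + s·p1
- Spurious OR = [pc / (1 − pc)] / [b / (1 − b)]

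**Lowest corner of the main range** (b = 10%, s = 10%, R = 1.5):
- p1 = 0.15/1.05 = 0.1429
- pc = 0.090 + 0.0143 = 0.1043
- OR = (0.1043/0.8957)/(0.10/0.90) = 1.05

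**Middle** (b = 5%, s = 20%, R = 2):
- p1 = 0.10/1.05 = 0.0952
- pc = 0.040 + 0.0190 = 0.0590
- OR = 1.19

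**Highest corner** (b = 5%, s = 40%, R = 2.5):
- p1 = 0.125/1.075 = 0.1163
- pc = 0.030 + 0.0465 = 0.0765
- OR = (0.0765/0.9235)/(0.05/0.95) = 1.57

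**Grid.** Each cell gives the spurious OR and, in brackets, the chance of a significant positive result with 800 v 2,000. That chance comes from a two-proportion test, and its nominal value is 2.5%. Ranges run over b = 5% and 10%.

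| R | s = 10% | s = 20% | s = 40% |
|---|---|---|---|
| 1.3 | 1.03 (4%) | 1.06 (5-6%) | 1.12 (9-13%) |
| 1.5 | 1.05 (5%) | 1.10 (8-10%) | 1.19-1.20 (17-27%) |
| 2.0 | 1.09-1.10 (7-10%) | 1.19 (17-25%) | 1.38-1.39 (48-70%) |
| 2.5 | 1.13-1.14 (11-15%) | 1.27-1.28 (30-45%) | 1.55-1.57 (76-93%) |

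The OR exceeds 1 whenever R exceeds 1. Its size depends mainly on s and R and hardly on b.

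**After restriction.** If the cases compared have no cardiovascular disease (s = 0), then pc = b, the OR by this route is 1.00 and the chance of a positive result is the nominal 2.5%.

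**Price of restriction.** Removing 10-40% of cases leaves 800 × 0.9 = 720 to 800 × 0.6 = 480. The OR detectable with 80% power at two-sided 0.05 rises from 1.43 to 1.45-1.54 if b is 10%, and from 1.61 to 1.64-1.75 if b is 5%.

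**The case against.** **The protocol does not specify a CHIP comparison with donors.** The primary endpoint is germline only, and the somatic endpoint names HCC. HCC versus non-HCC within cases is a natural reading and avoids donor selection altogether. This stands as a limit on the point, but does not remove it. The objectives in sections 2.1 and 2.2 take in somatic variants and advanced MASLD, and section 5.2 leaves the comparator open.

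**The term for the excluded diseases is undefined.** Section 3.3 names neither cardiovascular nor blood disease. That is so. The link to donor eligibility makes the reading reasonable, not certain, and any affected controls who remain would shrink the bias.

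**The size is assumed throughout.** A reader might infer that CHIP will look associated with advanced MASLD through other disease alone. The documents do not support that: they give none of the inputs, and mild ones leave an OR of 1.03 or less.

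**The covariates are not the fault.** It is tempting to say that age, sex, BMI and ancestry fail to correct this. Section 4.3 states them for the germline model. It states no CHIP association model, and that detail may properly sit in an analysis plan.

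**Blood neoplasms.** A reader might infer that section 4.2 records them, or that such cases will be counted as CHIP. It names cardiovascular comorbidity, and oncological treatment for HCC, but no blood neoplasm. The blood count is listed for controls only. Section 4.3 gives a gene panel and three callers but no rule on overt blood disease, so neither inference is established.

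**Conclusion.** The point holds as a bias in direction, with a size that the protocol does not allow anyone to fix. The one-sided exclusion and the protocol's own association of CHIP with leukaemia and cardiovascular disease together push any case-donor CHIP comparison upward. Over the main assumed range the false association runs from trivial to large enough to be declared significant more often than not.

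This rests on three things: the excluded chronic diseases include cardiovascular disease, few or no controls have it, and CHIP and that disease are positively associated. The haematological route is not quantified, because nothing in the document allows it.

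The point does not touch the germline primary endpoint, nor an HCC comparison made within cases. It deserves correction before analysis because the remedy is cheap and the misreading would concern a stated objective.

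**What to change.** For the CHIP analyses only:

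1. **Known haematological malignancy.** Do not count a case with such a history as CHIP, using the recorded medical history.
2. **Case-donor comparison.** Report any such comparison also in cases without recorded cardiovascular disease, using the comorbidity data in section 4.2. Do not interpret an association as a contribution to MASLD unless it persists there.
3. **HCC endpoint (section 5.2, item 1).** State the comparison as HCC versus non-HCC within cases. Add a sensitivity analysis limited to blood drawn before oncological treatment, where dates allow. The samples were collected earlier under other studies, and no rule on the timing of the draw relative to treatment is stated. The protocol does not say that treatment alters CHIP, so this is a precaution.

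Do not impose the whole control restriction on cases: read literally, it would also remove those with drug-treated type 2 diabetes. Nor should all cases treated before the draw be dropped from the main analysis, since that would deplete the HCC group which the endpoint studies.

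**Cost.** These are analysis-set rules with no new recruitment or sampling. The restricted analyses have fewer cases and lower precision, as quantified above for the case-donor comparison; the loss of HCC cases in the sensitivity analysis cannot be estimated from the document. Haematological history may be incomplete, because section 4.2 does not name it. Chronic diseases other than cardiovascular ones remain unbalanced. The germline analysis is unchanged.

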## **4. PROCEDURES RELATING TO THE STUDY**

### **4.1 Patient recruitment**

Patient enrollment will take place at the outpatient clinics of the Transfusion Medicine Unit of the Fondazione IRCCS Ca' Granda Ospedale Maggiore Policlinico during routinely scheduled visits.

If obtaining consent for the clinical study is not compatible with the conduct of the study, consent will be obtained remotely via telephone, as described in chapter 9.2.3.

In all other cases, the informed consent process will be managed in person.

Patients who enroll in the DETECTIVE study will not undergo any additional procedures, but will consent to the use of data and biological samples previously collected in the SERENA, REASON, and Liver-Bible studies.

### **4.2 Sample and data collection**

Our research is based on two fundamental pillars, represented by rigorously selected study cohorts.

The SERENA project involves 800 patients with advanced MASLD, whose peripheral blood DNA will be sequenced (WGS, 20x coverage). To further deepen our understanding of disease progression, a subset of 35 of these patients will undergo even more detailed analysis: we will sequence at 50x 80 pathological liver tissue samples from the REASON study, including samples with advanced fibrosis and, where present, hepatocellular carcinoma (HCC).

On the control side, the Liver-BIBLE Milano project offers us a valuable cohort of 2,000 individuals matched by sex and metabolic risk factors. These participants are selected from blood donors aged 40 to 70 years who meet at least two criteria for metabolic syndrome. Their phenotypic characterization is extremely thorough, ranging from anthropometric assessment to metabolic and inflammatory profiles, from noninvasive liver injury diagnostics to OMICs analysis. This integrated approach, combining genetic and clinical data from well-defined cohorts, will allow us to conduct robust comparisons between cases and controls, significantly advancing our understanding of advanced MASLD.

Specifically, biological samples will be collected as follows:

- Peripheral Blood: Peripheral blood DNA samples will be collected from all 800 MASLD patients and all 2000 metabolic controls.
- Pathological Liver Tissue: A total of 80 pathological liver tissue samples will be collected from a subset of 35 patients with advanced MASLD. These samples will be derived from the REASON study and will include tissue with advanced fibrosis (n=30) and, when present, hepatocellular carcinoma (HCC) samples (n=12).

Clinical and phenotypic data associated with the biological samples collected:

- For Patients with Advanced MASLD, aimed at understanding the progression of the disease, its complications and related factors:

- Detailed Clinical Phenotype: Includes a detailed medical history focused on the history of MASLD, including diagnosis, progression, presence and severity of specific symptoms, history of pharmacological or surgical treatments, and relevant comorbidities, particularly metabolic and cardiovascular ones.
- Biomarkers of Liver Injury and Function: Liver enzymes such as alanine aminotransferase (ALT), aspartate aminotransferase (AST), gamma-glutamyl transpeptidase (GGT), and alkaline phosphatase (ALP) levels, indicators of hepatocellular injury or cholestasis.
- Liver synthetic function: Bilirubin, albumin, prothrombin time/INR, which reflect the liver's synthetic capacity.
- Non-invasive biomarkers of liver damage: data from tools such as Fibroscan or predictive score calculations (e.g., FIB-4, NAFLD Fibrosis Score) to assess the presence and degree of steatosis, steatohepatitis (NASH), fibrosis, and cirrhosis.
- Metabolic Risk Factors: such as data on glucose, lipids (total cholesterol, HDL, LDL, triglycerides), insulin, HbA1c and indices of insulin resistance (e.g. HOMA-IR), which are essential for outlining the metabolic profile underlying MASLD.
- Inflammatory Biomarkers: Such as C-reactive protein (CRP) and ferritin, useful for assessing systemic and/or hepatic inflammatory status.
- Hepatocellular Carcinoma (HCC) Data: For patients who have developed HCC, specific information on diagnosis, staging, oncological treatments and follow-up is collected, essential for studying clonal evolution.

- For Metabolic Controls, aimed at providing an extremely in-depth baseline characterization of their general health and metabolic risk profile, in the absence of advanced MASLD, to serve as a robust comparison:
  - Detailed Anthropometric Assessment: Height, weight, waist circumference, BMI, for a precise quantification of adiposity.
  - Detailed Medical History: Lifestyle, eating habits (diet), complete medical history, with particular attention to the presence of metabolic risk factors (hyperglycemia, hypertension, dyslipidemia, increased adiposity) which are inclusion criteria.

- Complete Blood Count: Evaluation of the cellular components of the blood.
- Coagulation Parameters: Includes factors such as FVIII, VWF, protein C (PC) and D-dimer.
- Standard Clinical Biochemistry: Includes assessments of general liver and renal function, as well as inflammatory biomarkers.
- Complete Metabolic Profiles: Glucose, lipids (total cholesterol, HDL, LDL, triglycerides), insulin and HbA1c, to quantify metabolic risk factors.
- Liver Biomarkers: Although not targeted to progression of advanced MASLD, baseline biomarkers of liver function are included to ensure the absence of significant non-MASLD liver disease.
- Non-Invasive Liver Injury Assessment (Fibroscan): Essential to confirm the absence of significant liver fibrosis in these controls, although they may have steatosis or early NASH.
- OMIC characterization (in a subset): This is a distinctive feature of this cohort, which includes circulating lipidomics, metabolomics, and metagenomics. It provides a very high level of molecular detail on their metabolic profiles and gut microbiome, crucial for understanding gene-environment-metabolism interactions.
- Prospective Follow-up Assessments: The longitudinal nature of the Liver-BIBLE Milano study means that follow-up data will be updated over time, providing information on the evolution of their metabolic and health status.

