#### 4.3 Sample analysis

The genetic analyses for this study will be conducted in close collaboration and under the supervision of Human Technopole.

As anticipated, the methodology envisaged for conducting this study involves whole-genome sequencing on DNA derived from peripheral blood (20x coverage) and pathological liver tissue (50x coverage) to characterize the genetic and somatic variants that influence disease progression.

The DNA will be isolated at the Foundation and shipped to the National Facility (NF) in batches of 3-4 plates at a time.

To identify associations between individual genetic variants and the burden of likely loss-of-function (LoF) variants at specific genetic loci, comparing participants with advanced MASLD to controls, analyses will be performed using a genome-wide regression model implemented in REGENIE, with additive genetic models accounting for age, sex, body mass index (BMI), and ancestry (BWI 1-10). To ensure the robustness of the results, the genome-wide significance threshold will be set at  $p < 5E-8$ . If the study is not powered to identify new significant associations, suggestive hits ( $p < 5E-6$ ) will be replicated in additional cohorts.

In addition to defining the risk of advanced MASLD compared to controls as the primary outcome, we will thoroughly examine the genetic contribution to various endophenotypes. These will include metabolic risk factors (such as insulin resistance indices), liver enzymes (AST, ALT, GGT), and indicators of liver damage (noninvasive predictors of steatosis, steatohepatitis, fibrosis, cirrhosis, and HCC). The results of these analyses will be crucial for improving risk stratification and identifying specific disease subphenotypes through the development of polygenic risk scores, which have previously proven effective in identifying subsets of patients at specific risk for liver or cardiovascular events. This approach will also aim to identify therapeutic targets with a high probability of clinical success.

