### 5.2 Secondary Endpoints

Other main endpoints of the study in question are:

- 1) Identification of somatic mutations in hepatocytes and hematopoietic cells in order to study their association with the development of HCC.
- 2) Use of PRS (existing in the literature and new) in predicting patterns of advanced MASLD among cases and controls
- 3) Analysis of the association between genetic variants and clinical and biological phenotypes of MASLD, considering metabolic markers, liver enzymes (AST, ALT, GGT) and non-invasive indicators of steatosis and fibrosis (Fibroscan)
- 4) Identification of functional variants (e.g. LoF) in genes involved in lipid metabolism, liver inflammation, oxidative stress associated with advanced MASLD.

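### Does excluding drug-treated diabetes from the controls only undermine the description of them as matched on metabolic risk factors?

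*Protocol*

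**What the plan says.** - Protocol section 4.2 calls the controls "a valuable cohort of 2,000 individuals matched by sex and metabolic risk factors". It then describes them as donors meeting at least two metabolic-syndrome criteria. It gives no matching procedure and no list of matched variables.
- Section 3.2 requires controls to have BMI above 25 and at least two of three further factors. The glycaemic factor is a single category, "impaired fasting blood glucose or diabetes mellitus".
- Section 3.3 excludes donors with chronic degenerative disease, "with the exception of well-controlled hypertension and type 2 diabetes mellitus not requiring pharmacological therapy". It links this to the usual rules for blood donation.
- Cases (sections 3.2 and 3.3) are selected on fibrosis or hepatocellular carcinoma and excluded for other liver diseases. Nothing limits diabetes treatment.
- Section 4.3 plans regression "with additive genetic models accounting for age, sex, body mass index (BMI), and ancestry". Diabetes is not a listed covariate.
- Section 5.2 includes as a secondary endpoint "Use of PRS (existing in the literature and new) in predicting patterns of advanced MASLD among cases and controls".

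**The concern.** A reader who sees that controls are matched on metabolic risk factors may assume that diabetes is balanced between the groups. Read with the eligibility rules, that cannot hold for treated diabetes: the control share is zero by design, while the case share is unrestricted and probably not small. None of the covariates in section 4.3 represents this difference directly.

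A variant that raises diabetes risk but has no effect on the liver could then appear more often in cases partly because of how controls were chosen. For single variants the genome-wide threshold gives strong protection. Polygenic scores are more exposed, because they add up many small effects and would be developed and evaluated in these same groups. The natural response would be to correct the matching statement, tabulate diabetes treatment by group and add a sensitivity analysis without drug-treated participants.

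**Working it through.** **1. Is there a contradiction?** Section 4.2 speaks of metabolic risk factors. Section 3.2 defines the glycaemic factor as impaired fasting glucose or diabetes together, and groups can be matched on that category whatever the treatment. Section 3.3 rules out matching only at a finer level, which section 4.2 never claims.

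**2. Inputs.** From the protocol: 800 cases, 2,000 controls, and thresholds 5E-8 and 5E-6 (taken as two-sided). Assumed, because the protocol gives none:
- allele frequency 0.3 with normal glucose and no liver effect;
- per-allele diabetes OR 1.2 to 1.4;
- 15 to 25% of controls diabetic without the exclusion, 5 to 10% with it;
- 50 to 70% of non-diabetic controls with impaired glucose, variant OR 1.1 to 1.2 for that state.

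The contrast is between controls without and with the exclusion, which isolates the eligibility rule from any natural excess of diabetes in cases.

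**3. Single variant.** The group frequency is a mixture of normal, impaired and diabetic strata, and z = ln(OR) × sqrt(2p(1−p) × 571.4), where p is the control frequency and 571.4 = 800 × 2000 / 2800.

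High end (diabetes OR 1.4, impaired OR 1.1, 50% impaired, 25% against 5% diabetic):
- stratum frequencies are 0.300 normal, 0.320 impaired and 0.375 diabetic;
- without the exclusion, 0.25 × 0.375 + 0.75 × (0.5 × 0.320 + 0.5 × 0.300) = 0.326;
- with it, 0.05 × 0.375 + 0.95 × (0.5 × 0.320 + 0.5 × 0.300) = 0.313;
- from unrounded frequencies, OR = 1.061, z = 0.93, and the chance of p < 5E-6 is 0.00014 (0.014%).

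| Scenario | OR |
|---|---|
| Diabetes OR 1.4, with impaired glucose | 1.011 to 1.061 |
| Diabetes OR 1.2, impaired OR 1.1 | 1.006 to 1.028 |
| Diabetes OR 1.4, no impaired-glucose allowance | 1.018 to 1.072 |
| Diabetes OR 1.2, no impaired-glucose allowance | 1.009 to 1.038 |

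The worst row (1.072) has at most a 0.03% chance of reaching 5E-6.

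**4. Polygenic score.** Assume an advanced-MASLD score correlates 0.1 to 0.5 with a diabetes score on which diabetics lie 0.4 to 0.6 SD higher. The eligibility gap is 0.05 to 0.20 (from 15 − 10% and 25 − 5%).
- Smallest shift: 0.1 × 0.4 × 0.05 = 0.002 SD.
- Largest shift: 0.5 × 0.6 × 0.20 = 0.06 SD.
- AUC = Φ(shift/√2) = 0.501 to 0.517.

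**5. What a restricted run could show.** Section 3.3 already keeps treated diabetes out of controls, so the run drops cases only. Assume a share f = 0.2 to 0.5 of cases is treated, leaving 640 to 400.
- The factor 571.4 falls to 484.8 or 333.3, so the standard error rises by sqrt(571.4/484.8) = 1.09 or sqrt(571.4/333.3) = 1.31.
- Power at 5E-8 for OR 1.5 and allele frequency 0.3 falls from 80% to 63% or 26%.
- For a fixed score, the change in the case-control mean difference has SE = f × sqrt(1/n_treated + 1/n_untreated). That is 0.2 × sqrt(1/160 + 1/640) = 0.018 to 0.5 × sqrt(1/400 + 1/400) = 0.035, a 95% half-width of 0.035 to 0.07 SD.
- The expected change is f × correlation × (0.4 to 0.6): from 0.2 × 0.1 × 0.4 = 0.008 to 0.5 × 0.5 × 0.6 = 0.15 SD. Most of it can be natural excess of treated diabetes in cases.

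At f = 0.5 the whole eligibility shift (0.002 to 0.06 SD) lies within the half-width. At f = 0.2 only its upper part exceeds it.

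**The case for a change.** The strongest case for a change needs no assumption about prevalence. The matching statement is in the protocol, describes who the controls are and supports the claimed robustness of the comparison, so no separate analysis plan could make it more accurate. No matching method is given, and section 6.1 says the numbers came from maximum availability, which does not sound like matched sampling. The preliminary GWAS (section 6.1, Graph 3) adjusted for presence of diabetes, so the sponsor has treated it as relevant. The data appear to be at hand: section 4.2 lists for cases "history of pharmacological or surgical treatments, and relevant comorbidities, particularly metabolic and cardiovascular ones", and for controls a medical history "with particular attention to the presence of metabolic risk factors (hyperglycemia, hypertension, dyslipidemia, increased adiposity) which are inclusion criteria".

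A larger figure is also possible. If 20 to 60% of cases are treated against 0% of controls, a variant with a treated-diabetes OR of 1.1 to 1.4 shows a case-control OR of 1.02 to 1.23, with up to a 10.3% chance of p < 5E-6.

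Part of this stands. Section 4.2 should be clearer about what was matched. The larger figure does not size the eligibility problem, because it counts the whole treated share in cases, including any excess that belongs to the disease. The preliminary GWAS had a different outcome (an FNI-defined one), so its covariates do not show that the planned model is wrong. Diabetes may lie on the path to advanced MASLD, so adjusting for it or restricting on it could remove real signal; treated diabetes also has no control counterpart to adjust against. A sensitivity analysis and a table by treatment are matters commonly left to the statistical analysis plan, which is not shown.

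**Conclusion.** No change to the plan is called for. The asymmetry is real and section 3.3 discloses it openly, with its reason. The matching phrase is loose, but it is compatible with matching on the broad category of section 3.2. The primary model is not at fault.

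Under the stated assumptions the eligibility rule alone produces an OR of about 1.01 to 1.06 (up to 1.07 without the impaired-glucose allowance), with at most a 0.014% (0.03%) chance of a suggestive hit. The score shift is worth an AUC of 0.50 to 0.52. The diabetes shares, variant effects and score correlation are all assumed, so the true effect on an advanced-MASLD score is unknown. The restricted run would not settle it: its precision is about as wide as the shift sought, or wider, it conditions on a possible mediator, and it cannot tell eligibility from natural excess. As an exploratory analysis it is optional.

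What remains is missing detail that the study report can supply: the factors actually matched, and the fact that drug-treated diabetes is excluded from controls only.
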